### **Subject drop out or withdrawal procedures**

If a subject drops out or we withdraw them from the study, the study team will:

- Update the tracking database to indicate that no further patient-self report data collection or participant contact will occur. They will not be asked to complete any more surveys. If we withdraw the participant from the study, we will send them a letter notifying them that they are no longer enrolled in the study.
- We will continue to use the data they have already contributed/agreed to allow us to use per their consent for analyses
- All participants using buprenorphine for treatment of OUD will be withdrawn from the entire study. We may learn about buprenorphine use from the screening survey or as indicated in VDW medication dispensing data ascertained prior to the analyses. Primary data collection will cease and they will not be included in analyses. This is an exclusion criteria.
- All pregnant women will be withdrawn from the study entirely. Primary data collection will cease and they will not be included in analyses. Pregnancy status will be determined via a screening question and diagnosis codes from the VDW for subjects in both study arm prior to analyses. We expect very few young women to be in the study due to the average age of chronic high dose opioid users at KP.

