## Subject drop out or withdrawal procedures

If a subject drops out or we withdraw them from the study, the study team will:

- Update the tracking database to indicate that no further patient-self report data collection or participant contact will occur.
- We will continue to use the data they have already contributed/agreed to allow us to use per their consent for analyses
- We will not ask them to complete any additional surveys or attend study visits (if applicable)

In rare instances, the study PI's may decide to withdraw a participant from the study and analyses. The reasons for removing participants from the study and analyses would be:

- Concern about data validity. Examples of the types of scenarios are when a participant's behavior indicates that they may not be answering questions truthfully either due to deceit, they are high on drugs during their scheduled visit or there is a medical condition like narcolepsy that makes it difficult for them stay awake during their scheduled appointment.
  - The research interventionist would bring concerns about data validity to the study team and the PI would make the determination on whether to withdraw or not. The study team will send them a letter informing them of their withdrawal.
- All participants using buprenorphine for treatment of OUD will be withdrawn from the entire study. Primary data collection will cease and they will not be included in analyses. While buprenorphine is a partial opioid, it is indicated for the treatment of opioid use disorder and rarely if ever used to treat pain at KPWA. Patients treated with buprenorphine for OUD are complicated and are either no longer on other opioids or being tapered off other opioids by the provider treating their OUD. They are not part of our study population of interest and thus buprenorphine use is both an exclusion criteria and reason for being withdrawn from the study.
  - If the research interventionist learns that the participant is taking buprenorphine for OUD, they would bring that information to the study team and the PI would withdraw the participant from the study. The study team will send them a letter informing them of their withdrawal.
  - Similarly, patients in both the intervention and control arm will be removed from the entire study and analyses if they are using buprenorphine as indicated in VDW medication dispensing data ascertained prior to the analyses.

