### **Study Procedures –Control Arm**

#### **Sequential description**

Participants randomized to the control arm (i.e. usual care only) will not receive any intervention visits. They will only complete the three surveys described above in the “Study Procedures – Intervention Arm and Control Arm” section.

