##### **a. Data Analysis**

Describe the data analysis plan, including:

- Statistical procedures.
- When applicable, the power analysis.
- Any procedures that will be used for quality control of collected data.

We will use descriptive statistics to characterize the sample at baseline. To address the trial's effectiveness aims, we will use an intent-to-treat approach (i.e., individuals will be analyzed according to randomized group regardless of participation in any opioid taper support sessions). We will also use a complete case analysis (i.e., that includes those participants who have observed follow-up outcome data) since we expect at least 85% follow-up at 12 months (primary time-point).

To compare each of the primary outcome measures (opioid dose and PEG score) between intervention groups the following linear regression model will be constructed:  $E(Y_{ij}) = \beta_0 + \beta_1 Trt_i + \beta_2 Time_j + \beta_3 Trt_i \times Time_j + \alpha_z Z_i$ , where  $Y_{ij}$  is the outcome for person  $i$  at time  $j$  ( $j=6$  or 12 months),  $Trt_i$  is the dichotomous intervention effect of interest (with control arm as the referent group),  $Time_j$  is the dichotomous variable indicating the 6- or 12-month time point,  $Trt_i \times Time_j$  is the interaction between the treatment and time point indicators and  $Z_i$  is a vector of baseline covariates that we a priori plan to adjust for including age, gender, baseline opioid dose group, whether they were referred to COMET, and KPWA clinic. We will include both 6- and 12-month time-points in a single model to improve statistical efficiency, but the 12-month time point is considered primary. We will fit the linear regression model using GEE with robust standard errors to account for the multiple time points in a single model. We will use two-sided tests at the 0.05 level. Arguments against adjusting for multiple comparisons for two co-primary outcomes have been made by Rothman and others. (Rothman KJ. No adjustments are needed for multiple comparisons. *Epidemiology*. 1990;1:43–46) For each outcome, we will report the adjusted mean difference between treatment groups and its 95% confidence interval.

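### Randomised participants are deleted from the analyses for buprenorphine use, including use that starts during follow-up, although the plan states intent-to-treat

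*Combined protocol and SAP*

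**What the plan says.** Section 6a (Data Analysis) states the principle: "we will use an intent-to-treat approach (i.e., individuals will be analyzed according to randomized group", whatever the attendance at sessions. It adds a complete-case analysis and does not mention any removal of randomised participants.

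Two withdrawal sections say something different. For both arms (Study Procedures – Intervention Arm and Control Arm), participants using buprenorphine for OUD are withdrawn: "Primary data collection will cease and they will not be included in analyses". The sources named there are these: "We may learn about buprenorphine use from the screening survey or as indicated in VDW medication dispensing data ascertained prior to the analyses". The intervention-arm section repeats the rule and extends it: "Similarly, patients in both the intervention and control arm will be removed from the entire study and analyses if they are using buprenorphine". It describes the rule's role, "thus buprenorphine use is both an exclusion criteria and reason for being withdrawn from the study", and says that these patients "are either no longer on other opioids or being tapered off other opioids by the provider treating their OUD". It also adds a second source: "If the research interventionist learns that the participant is taking buprenorphine for OUD, they would bring that information to the study team". The control arm has no such contact, because its participants "will not receive any intervention visits".

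The same intervention-arm list lets the PI remove a participant from the analyses over doubts about data validity, on concerns raised by the interventionist. Both sections also carry a general rule that data already contributed under the consent stay in use after withdrawal.

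**The concern.** An intent-to-treat comparison is protected because membership of the analysis set is fixed at randomisation. Here membership can depend on something that happens afterwards and that is bound up with a co-primary outcome: by the protocol's own account, a person who starts buprenorphine for OUD is leaving other opioids, and daily opioid dose is what the trial measures. An intervention that discusses opioid history and tapering could plausibly change how often buprenorphine is started, although that is inference and the documents do not say so.

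Finding the cases is also not fully symmetric. The dispensing check covers both arms, but the interventionist route exists in one only. The data-validity removal starts with the interventionist and ends with a PI decision, so in practice it too reaches only the intervention arm. The sensitivity analyses in section 6a add baseline covariates or, if follow-up is below 85%, impute for non-response. Neither puts the deleted people back.

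**Working it through.** **Does the rule reach use that starts after randomisation?**

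1. Section 5b already excludes people taking buprenorphine for OUD, and screening precedes randomisation.
2. The intervention-arm section names withdrawal as a reason in addition to that exclusion.
3. The interventionist can be the one who finds the use. Under the intervention-arm Sequential description, the calls start only after randomisation.
4. The reference to data ascertained before the analyses dates the data pull, not the use. No section sets a cut-off at randomisation.

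Points 2 and 3 carry the reading; point 4 shows that nothing contradicts it.

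**Scale of the design.** The Sample Size section assumes a baseline mean of 67 mg, a 20 mg difference and an SD of 34 mg. Its figures reproduce: 20/67 = 29.9% (stated as 30%), and 86 per arm gives 97.0% power for dose by the two-sample t-test (stated as above 90%). They do not bear on the concern and only set its scale.

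- Means among people kept: control 67 mg (assumed unchanged from baseline), intervention 67 − 20 = 47 mg, difference −20 mg.
- Section 5a plans 125 per arm, and section 6a expects 85% follow-up: 125 × 0.85 = 106.25. SE = 34 × √(2/106.25) = 4.66 mg. With the Sample Size section's target of 215, 215 × 0.85/2 = 91.4 per arm and SE = 34 × √(2/91.4) = 5.03 mg.

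**Effect of deletion on dose.** Let pI and pC be the shares starting buprenorphine in the intervention and control arms, and m the starters' 12-month dose of other opioids. The documents give none of these, so all are assumptions.

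Full-set difference = (1 − pI)·47 + pI·m − (1 − pC)·67 − pC·m = −20 − (47 − m)·pI + (67 − m)·pC

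After deletion the analysis reports −20.

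| pI / pC | Full set, m = 0 | Full set, m = 20 |
|---|---|---|
| 5% / 2% | −21.01 | −20.41 |
| 5% / 4% | −19.67 | −19.47 |
| 2% / 2% | −19.60 | −19.60 |
| 5% / 5% | −19.00 | −19.00 |
| 2% / 5% | −17.59 | −18.19 |

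At m = 0, deletion runs from understating benefit by 1.01 mg to overstating it by 2.41 mg (2.41/4.66 = 0.52 SE). At m = 20 the range is 0.41 mg understated to 1.81 mg overstated. The sign changes at pI/pC = (67 − m)/(47 − m), which is 1.43 at m = 0 and 1.74 at m = 20.

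**A different assumption about starters.** In general the shift is −(pI·gI − pC·gC), where g is the mean dose of those removed minus that of those kept. The table at m = 0 has gI = −47 and gC = −67. If the gap g is the same in both arms, the shift is −(pI − pC)·g. For g from −30 to −60 mg, 5% vs 2% gives +0.9 to +1.8 mg (towards no effect), 2% vs 5% gives −0.9 to −1.8 mg, and equal shares give 0.

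**Data-validity removal.** If a share p of the intervention arm is removed and those people were at 67 mg rather than 47 mg, the shift is p × 20: 0.2 mg at p = 1% to 0.8 mg at p = 4% (125 × p = 1.25 to 5 people). This favours the intervention; the sign reverses if those removed had lower doses than those kept.

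**The case against.** The strongest reply is that section 6a explains intent-to-treat only in terms of session attendance, pairs it with complete cases, and never says that every randomised person will be analysed. The exclusion is pre-specified, has a stated reason (these patients lie outside the population of interest), and is checked in both arms from one objective source. All of that is true, and it narrows the conflict to one between the intent-to-treat label and the removal rule. It does not remove it: complete-case analysis deals with outcomes that were not observed, whereas this rule discards people whatever was observed.

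It can also be said that the rule only mops up ineligible entrants, since the both-arms section adds that buprenorphine is an exclusion criterion. The separate withdrawal reason and the post-randomisation detection route do not fit that reading.

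On size the reply largely stands. The intervention-arm section calls PI removals rare. At the design effect even the most extreme row leaves the conclusion unchanged (17.59/4.66 = 3.8 SE), and nothing in the documents suggests more starts among controls. Scoring starters at 0 mg presumes that buprenorphine does not count in the morphine-equivalent dose, which is not stated.

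Four stronger readings are tempting but unsupported:

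- A reader might infer that any buprenorphine record in the 2016–2022 dispensing data triggers deletion. The rule is worded in terms of current use.
- A reader might infer that buprenorphine for any indication is covered, because the both-arms sentence omits OUD. It sits under a bullet limited to OUD treatment.
- A reader might infer that detection is one-sided. Only use missing from the dispensing data is, and its frequency is unknown.
- A reader might group pregnancy with this point. Section 5c makes non-inclusion of pregnant women a human-subjects commitment, so it is a different matter.

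**Conclusion.** The concern holds. As written, the primary analysis can drop randomised participants because of an event after randomisation that is tied to the dose outcome, with one detection route and one discretionary removal that work in the intervention arm only. Such a result should not carry the intent-to-treat label.

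The numerical effect is probably small: under assumed starts of 2% to 5% per arm, at most about half a standard error for dose. A reader might infer that deletion flatters the intervention. The documents do not support that: the direction depends on unknown start rates and on how starters' doses compare with those of the people kept, and with equal shares and equal gaps the shift is zero. Nor do they show which way any data-validity removals would push the result. The case for change rests on the contradiction and on how little it costs to resolve, not on a demonstrated bias.

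**What to change.** For the primary analysis:

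- Exclude for buprenorphine only those whom VDW dispensing shows to have been taking it for OUD at randomisation, that is, people who did not meet the section 5b criterion at entry. Apply this identically in both arms, by someone masked to arm.
- Keep all other randomised participants in their assigned arm, using the outcome data available under their consent. Dose can come from dated VDW dispensing if that is the source of the dose outcome, which the protocol should state.
- Do not delete participants over data-validity concerns.
- Pre-specify how buprenorphine counts in the dose outcome.
- Report buprenorphine initiation and all removals by arm, and run the current exclusions as a sensitivity analysis.

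Reconcile both withdrawal sections with section 6a, including the general rule on keeping contributed data. Pregnancy handling, and whether participation or contact stops, remain for the protocol and the IRB.

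The costs are an amendment with IRB approval, a scoring rule for buprenorphine, one added sensitivity analysis, and a few heterogeneous participants or less reliable survey answers kept in. Dated dispensing is already collected for both arms. PEG cannot be recovered where survey contact stops. If 2% to 5% of the intervention arm and no controls lost later PEG, and those lost were 2.5 points worse (both assumed), PEG would still be flattered by 0.02 × 2.5 = 0.05 to 0.05 × 2.5 = 0.125 point, against an SE of 2.5 × √(2/106.25) = 0.34. PEG missingness after withdrawal should therefore be reported by arm.

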## Anticipated study end date

The anticipated study end date for the completion of primary analyses will be on or before December 31, 2021

### **Study Procedures –Control Arm**

#### **Sequential description**

Participants randomized to the control arm (i.e. usual care only) will not receive any intervention visits. They will only complete the three surveys described above in the “Study Procedures – Intervention Arm and Control Arm” section.

#### **Device/drug information**

N/A

#### **Secondary data: data, sources, and date range**

N/A – no additional data other than what is described in the “Study Procedures – Intervention Arm and Control Arm” will be collected.

#### **Alternative treatment(s) and/or denied treatment**

N/A

#### **Deception/incomplete disclosure**

N/A

#### **Incidental findings**

N/A

#### **Procedures to monitor, lessen or mitigate risk**

N/A

#### **Subject drop out or withdrawal procedures**

If a subject drops out or we withdraw them from the study, the study team will:

- Update the tracking database to indicate that no further patient-self report data collection or participant contact will occur.

#### **Anticipated study end date**

The anticipated study end date for the completion of primary analyses will be on or before December 31, 2021

##### **a. Data Analysis**

Describe the data analysis plan, including:

- Statistical procedures.
- When applicable, the power analysis.
- Any procedures that will be used for quality control of collected data.

We will use descriptive statistics to characterize the sample at baseline. To address the trial's effectiveness aims, we will use an intent-to-treat approach (i.e., individuals will be analyzed according to randomized group regardless of participation in any opioid taper support sessions). We will also use a complete case analysis (i.e., that includes those participants who have observed follow-up outcome data) since we expect at least 85% follow-up at 12 months (primary time-point).

To compare each of the primary outcome measures (opioid dose and PEG score) between intervention groups the following linear regression model will be constructed:  $E(Y_{ij}) = \beta_0 + \beta_1 Trt_i + \beta_2 Time_j + \beta_3 Trt_i \times Time_j + \alpha_z Z_i$ , where  $Y_{ij}$  is the outcome for person  $i$  at time  $j$  ( $j=6$  or 12 months),  $Trt_i$  is the dichotomous intervention effect of interest (with control arm as the referent group),  $Time_j$  is the dichotomous variable indicating the 6- or 12-month time point,  $Trt_i \times Time_j$  is the interaction between the treatment and time point indicators and  $Z_i$  is a vector of baseline covariates that we a priori plan to adjust for including age, gender, baseline opioid dose group, whether they were referred to COMET, and KPWA clinic. We will include both 6- and 12-month time-points in a single model to improve statistical efficiency, but the 12-month time point is considered primary. We will fit the linear regression model using GEE with robust standard errors to account for the multiple time points in a single model. We will use two-sided tests at the 0.05 level. Arguments against adjusting for multiple comparisons for two co-primary outcomes have been made by Rothman and others. (Rothman KJ. No adjustments are needed for multiple comparisons. *Epidemiology*. 1990;1:43–46) For each outcome, we will report the adjusted mean difference between treatment groups and its 95% confidence interval.

A set of comparable linear regression models will be fit for continuous secondary outcomes. For dichotomous secondary outcomes, similar models will be built using a modified Poisson regression framework with a robust sandwich estimator to estimate adjusted relative risks and 95% confidence intervals. In addition, for each outcome, we will conduct a sensitivity analysis that further adjusts for baseline factors that are predictive of the outcomes, predictive of the probability of being missing at follow-up, or found to be significantly different between treatment groups. If more data are missing than expected (i.e., <85% with follow-up), we will also conduct a sensitivity analysis using an imputation method for non-ignorable non-response to evaluate whether our results are robust to different missing data assumptions. Selection bias analyses will compare demographic and clinical data of non-responders (potentially eligible per VDW and unreachable for recruitment) with responders (enrolled) using chi square and t-tests. This will allow us to identify factors associated with non-response. Secondary analyses will be conducted to assess for subgroup heterogeneity of treatment effects across levels of these pre-specified baseline variables: SUD+ vs SUD-, MH+ vs MH-, <90mg. vs >90mg MED, opioids with sedatives vs without, and focal pain vs multifocal pain. Heterogeneity will be indicated by a significant test of the interaction between treatment and each baseline variable, and subgroup-specific treatment effects with confidence intervals will be reported. In light of multiplicity and reduced power, these results of these analyses will be interpreted cautiously.

---

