### Screening, Randomization, and Follow-up

Potentially eligible participants will be identified by the study programmer using KPWA EHR data that located in the KPWHRI Virtual Data Warehouse. Potentially eligible patients will then be screened by phone twice for additional eligibility requirements before being consented and enrolled into the study. Eligible participants will be randomized based on their primary care clinic and baseline opioid dose into one of the trial arms. Both groups will be surveyed on physical health, pain, medication use, and mental health at baseline (prior to randomization), 6 months and 12 months. The total length of enrollment/follow-up in the trial for both groups is one year. See Figure 1 for the study process.

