### Study Procedures – Intervention Arm and Control Arm Sequential description

As described in the recruitment section of this application, potential research participants are identified via the KPWHRI VDW by the KPWA programmer and sent a letter of invitation, a study information sheet, study insert, and a \$2 incentive. Five days after the invite letter is sent, the KPWA survey team calls subjects for the first screening. Participants will be screened twice. First, they will be screened on basic eligibility criteria when the survey research program calls them to recruit. (See STRIPE screening

script for screening questions.) If the participant passes the first round of screening and is still interested, they will be scheduled for a second round of screening with a study research specialist.

Prior to the call, the study team will mail the participant a copy of the consent form and a cover letter. During the second screening call, the research specialist will ask sensitive eligibility questions regarding recent intent to harm and recent psychiatric hospitalization. (see "Pre-randomization script" for sensitive eligibility screening script and questions). If the participant passes this round of screening, the research specialist will administer and obtain oral consent. The participant will then be offered the baseline survey via phone or web. If phone is chosen, the participant will be asked if they would like to do the baseline survey now or schedule a time to complete it. If web is chosen, the research specialist will confirm the participants email address and email them a link to the survey. Reminder emails and/or phone follow-up will occur if subjects do not complete the baseline survey.

Once the baseline survey is complete, we will randomize the participant into the intervention arm or the control arm. The study team wants participants to be randomized after the baseline survey out of concern that knowledge of status could affect a subject's responses to questions and participation in the baseline assessment. We will send participants a thank you letter with their incentive upon completion of the baseline assessment that details which arm they were assigned to and next steps.

We anticipate the time from the letter being mailed to time of enrollment to be between 2-4 weeks. All invitation materials, consent forms, HIPAA authorization forms and scripts are attached in this package.

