After the baseline assessment and randomization, all participants will be asked to take two more surveys; 6 months after enrollment and 12 months after enrollment. The survey can be taken either in web form or on the telephone, administered by a survey research program telephone interviewer. With the 12 month phone or web survey reminder letter, all participants will receive a \$2 pre-incentive. The survey will ask questions about physical health (including any experience with pain), mental health (depression and anxiety), and medication use. All baseline, 6-month, and 12-month surveys including script are included in this packet. See Master Survey document for a list of the surveys to be administered at the three-time points.

Additionally, all subjects enrolled in the intervention who choose to taper their opioids arm will be asked to complete the two item Graded Chronic Pain Scale (GCPS) and the fourteen item Hospital Anxiety and Depression Scale (HADS) before each intervention telephone session. (See Measures for Intervention Arm only doc.). Surveys are attached in this package. The pre-visit GCPS and HADS will be completed on paper (mailed with intervention packet materials) prior to the visit and read their score to the research interventionist at the beginning of the session.

Activity	Time Commitment
----------	-----------------

Read invitation packet	5 minutes
1 st screening call	10 minutes
Read consent packet and answer any questions	10 minutes
2 nd screening call including consent and randomization	20 minutes
Baseline survey	30 minutes
Pre-visit GCPS and HADS for participants who choose to taper	5 minutes each visit 5-18
Intervention arm study visit 1-18	30-60 minutes each visit
6 month survey	20 minutes
12 month survey	20 minutes

We anticipate it will take 18 months to enroll all 250 study participants. Each participant will be followed for 12-months post randomization.

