**Sample Size:**

Our sample size is designed to ensure that we are highly powered to detect a clinically meaningful difference in the co-primary outcomes of opioid dose and pain (PEG) at 12 months. With 172 participants (86 per intervention arm) we will have >90% power to detect a 20mg mean difference in opioid dose between intervention groups assuming a 34 mg SD (based on data from KPWHRI participants meeting entry criteria) and a two-sided, two-sample equal-variance t-test. Assuming the mean baseline dose in our study population to be 67mg MED, this 20mg difference represents a clinically meaningful 30% reduction. Further, given our

sample size of 172 participants we will have approximately 90% power to detect a 1.2 point difference in the PEG between intervention groups, assuming a standard deviation of 2.5. To ensure adequate power given potential loss to follow-up we inflated our final sample size by 25% yielding a target randomization of 215 participants. This will also allow some pre-specified sub-group analyses to look for heterogeneity of treatment effect, as described below. Sample and power calculations were conducted using PASS software Version 14.

b. Sharing of Results with Subjects

Describe whether results (study results or individual subject results, such as results of standard or research lab tests and genetic tests) will be shared with subjects or their providers.

If the study carries a risk of incidental findings, describe your plan for evaluating these and determining whether and how subjects or their providers will be given this information.

If laboratory results will be shared with subjects or their healthcare providers, verify that the laboratory conducting the test is Clinical Laboratory Improvement Amendments (CLIA) certified. We will not be sharing study results with participants

We will be communicating some study information with providers, however we will not be sharing study results with the provider

- If a participant is enrolled in the intervention arm, the provider will be notified of their participation by the study team

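### The primary PEG model does not name baseline PEG as a covariate, so the main PEG estimate may be less precise than the data allow.

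*Combined protocol and SAP*

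**What the plan says.** Section 6a, Data Analysis, specifies one regression for both co-primary outcomes. The response is the value at 6 or 12 months, with terms for treatment, time and their interaction. It is fitted by GEE with robust standard errors, and 12 months is the primary time point. The covariate vector holds "baseline covariates that we a priori plan to adjust for including age, gender, baseline opioid dose group, whether they were referred to COMET", and the list ends with clinic. Baseline PEG is not on it.

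The same section adds that, for each outcome, "we will conduct a sensitivity analysis that further adjusts for baseline factors that are predictive of the outcomes", that predict missingness, or that differ significantly between arms. For the other continuous endpoints, "A set of comparable linear regression models will be fit for continuous secondary outcomes".

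On allocation, section 4 says: "Eligible participants will be randomized based on their primary care clinic and baseline opioid dose into one of the trial arms". PEG is not a randomisation factor. On timing, section 4 says: "Both groups will be surveyed on physical health, pain, medication use, and mental health at baseline (prior to randomization), 6 months and 12 months". Section 6 confirms the order: "Once the baseline survey is complete, we will randomize the participant into the intervention arm or the control arm". Neither place names the PEG as the baseline pain instrument. For the instruments, section 6 points elsewhere: "See Master Survey document for a list of the surveys to be administered at the three-time points".

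The Sample Size paragraph claims, with 86 per arm, "approximately 90% power to detect a 1.2 point difference in the PEG between intervention groups, assuming a standard deviation of 2.5". The only test it names is an unadjusted two-sample t-test.

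**The concern.** The baseline value of a continuous outcome is usually among its strongest predictors. The plan accepts this for opioid dose, which is adjusted for baseline dose group, but the shared list gives PEG no counterpart. Allocation does not balance PEG, and because follow-up values are modelled directly, the baseline is not used through a change score either.

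If the listed covariates are all that enters, variation in follow-up PEG that baseline PEG could explain stays in the residual. The headline interval for a co-primary outcome is then wider than it needs to be. A tighter estimate would probably appear in the sensitivity analysis, but as a supporting result with covariates that were not fixed in advance.

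The width of the PEG interval matters here. Section 2 aims to show that opioids can be tapered without more pain or activity interference, and how firmly the trial can say so depends on how tightly that interval excludes worsening.

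**Working it through.** **Inputs from the documents.** PEG difference 1.2 and SD 2.5; 86 per arm; target randomisation 215 (Sample Size). Two-sided 0.05 and at least 85% followed at 12 months (Data Analysis). Enrolment target 250 (sections 2 and 5a).

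**Assumed.** The correlation r between baseline and 12-month PEG is not given. I take 0.3, 0.5 and 0.7.

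**Step 1: the plan's own figure.** SE = 2.5 × √(2/86) = 0.381, and 1.2/0.381 = 3.15. The normal approximation gives Φ(3.15 − 1.96) = 88.3%, and the exact noncentral t gives 87.9%. The plan says approximately 90%. The figure is broadly reproduced, and it takes no credit for baseline adjustment.

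**Step 2: numbers followed.** 250 × 0.85 = 212.5, about 106 per arm. 215 × 0.85 = 182.75, about 91 per arm. The plan's evaluable target is 86 per arm.

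**Step 3: effect of adjustment.** Residual SD = 2.5 × √(1 − r²). The 95% half-width is t(0.975, 2n − 2) × residual SD × √(2/n). Power is from the noncentral t.

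| Per arm | | r = 0 (not adjusted) | r = 0.3 | r = 0.5 | r = 0.7 |
|---|---|---|---|---|---|
| 86 | half-width | 0.75 | 0.72 | 0.65 | 0.54 |
| 86 | power | 87.9% | 90.7% | 95.1% | 99.2% |
| 91 | half-width | 0.73 | 0.70 | 0.63 | 0.52 |
| 91 | power | 89.6% | 92.2% | 96.1% | 99.5% |
| 106 | half-width | 0.68 | 0.65 | 0.59 | 0.48 |
| 106 | power | 93.6% | 95.4% | 98.0% | 99.8% |

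The equivalent sample-size factor is 1/(1 − r²) = 1.10, 1.33 and 1.96.

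**Step 4: if the listed covariates already explain some PEG variance.** Assume they explain 10%, and read r as a partial correlation. Residual SD = 2.5 × √(0.9 × (1 − r²)). At 106 per arm the half-width goes from 0.64 to 0.61, 0.56 or 0.46, and power from 95.6% to 97.0%, 98.9% or 99.9%. The gain is somewhat smaller but remains.

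**Step 5: the planned two-time-point model.** The 6- and 12-month GEE with robust standard errors was simulated, 2,000 runs per setting. The plan leaves some details open, so these were assumed: independence working correlation, six covariates unrelated to PEG, and a correlation between the two follow-ups of 0.6 (0.7 when r = 0.7).

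| Followed in total | Half-width without baseline PEG | With it, r = 0.3 / 0.5 / 0.7 |
|---|---|---|
| 212 | 0.67 | 0.64 / 0.58 / 0.48 |
| 172 | 0.74 | 0.71 / 0.64 / 0.53 |

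Mean estimates were between −1.19 and −1.21 with and without adjustment, for a true difference of −1.2, so neither model is biased.

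**Step 6: chance imbalance is not a second harm.** At r = 0.7 and 106 per arm, 0.677² = 0.458 = 0.483² + 0.474². The last term, with 0.474 = 0.7 × 0.677, is the part due to chance baseline differences. It is already inside the unadjusted interval.

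**Step 7: skipped baseline items.** If 5% of baseline PEG values are missing at random and mean-imputed (an assumed rate), the adjusted half-widths at 212 followed are 0.64, 0.58 and 0.49. At 10% they are 0.64, 0.59 and 0.50. Nobody is dropped.

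**The case against.** Nothing in the plan breaks without this change. The PEG power was computed on the full SD of 2.5, and at 250 enrolled with 85% followed it is 93.6% with no baseline adjustment. The gain depends on a correlation the documents do not supply. At r = 0.2 and 106 per arm, power moves only from 93.6% to 94.4%. The covariate list opens with *including*, so baseline PEG is not excluded. The sensitivity analysis would probably bring it in, and the text does not say whether predictive factors will be picked from trial data or from prior knowledge. The documents also do not confirm that the PEG is in the baseline survey.

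Most of this stands and sets the limits of the point. The plan is valid, the stated power is not undermined, and the size of the gain is uncertain. What does not follow is that the matter is already settled. An open list leaves the analyst free to add or omit baseline PEG after seeing results. A sensitivity analysis that does not name it, however its factors are chosen, leaves the primary estimate uncommitted. The survey question is a reason to check the instrument before making the change.

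**Conclusion.** The concern holds, as a loss of precision and a gap in pre-specification. The primary PEG analysis is not committed to the covariate most likely to sharpen it. For assumed correlations of 0.3 to 0.7, the headline half-width at 106 per arm would be 0.03 to 0.19 points wider than necessary (0.68 against 0.65 to 0.48). At 86 per arm, adjustment would lift the reproduced power of 87.9% above 90% even at r = 0.3. The direction requires only a clearly non-zero correlation between repeated PEG scores; the size rests on the assumed values. There is no bias on average, and no stated design figure fails.

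Because continuous secondary outcomes use comparable models, the same gap applies to any of them measured at baseline. No effect was computed for those. The change should be made, but the trial's validity does not depend on it.

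**What to change.** Before outcome data by arm are seen:

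- In Data Analysis, name the continuous baseline PEG score in the covariate vector of the primary PEG model. Keep clinic and baseline dose group, which match the randomisation factors.
- For each continuous secondary outcome also measured at baseline (for example pain self-efficacy and depression symptoms, if they are surveyed then), name its own baseline value in its model.
- State a rule for missing baseline values, since section 6 lets participants skip questions. Mean imputation of the baseline covariate is enough, and it keeps everyone with an observed follow-up outcome in the complete-case set the plan defines.
- Confirm from the Master Survey document that the PEG items are asked at baseline.

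The cost is a few lines of analysis-plan text. No new data collection is needed if the PEG items are in the baseline survey. That survey is not among the documents reviewed, so this has to be verified.
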